#### 6.3.7.2.2 Severity Definition

Individual radiographic severity for microhemorrhages, leptomeningeal hemosiderosis and macrohemorrhages is defined in Table 6-4. ARIA-H radiographic severity is defined as the worst individual radiographic severity among microhemorrhages, leptomeningeal hemosiderosis and macrohemorrhages for an MRI scan as captured in its BMW. If any macrohemorrhages are present at an MRI scan, then the ARIA-H radiographic severity is severe. If macrohemorrhages are absent at an MRI scan, then the worse severity between microhemorrhages and leptomeningeal hemosiderosis will be the ARIA-H radiographic severity. For example, if there are 4 incident microhemorrhages, 1 incident areas of leptomeningeal hemosiderosis and no presence of macrohemorrhages on a BMW, ARIA-H is rated as "Moderate".

Table 6-4. Definition for Individual Radiographic Severity related to ARIA-H

Incident (CFB) Findings	Mild	Moderate	Severe
Number of microhemorrhages	1-4	5-9	10 or more
Areas of leptomeningeal hemosiderosis		1	2 or more
Presence of macrohemorrhages	_	_	Yes

Protocol No. AL002-2 Last Revision Date: 12 Aug 2025

## 6.3.7.2.3 Time to First Occurrence Definition

Definition is the same as the time to first occurrence definition for ARIA-E.

## 6.3.8 Neurological Examination

A complete neurologic examination including the evaluation of consciousness, orientation, cranial nerves, motor and sensory system, coordination and gait, and reflexes will be performed at scheduled visits (refer to the Schedules of Assessments in the protocol for scheduled visits). CFBs abnormalities should be recorded at each subsequent neurologic examination. New or worsened abnormalities should be recorded as an AE on the AE electronic CRF if considered clinically significant in the Investigator's opinion.

#### 6.3.9 Ophthalmological Examination

Ophthalmologic exams include the following:

- A visual acuity exam (e.g., using a Snellen chart)
- Slit-lamp examination before and after dilation
- Dilated exam of the fundus by indirect ophthalmoscopy
- Optical coherence tomography (OCT) exam, including enhanced depth imaging OCT for examination of the choroid

Ophthalmological assessments will be recorded at scheduled visits (refer to the Schedules of Assessments in the protocol for scheduled visits). CFBs abnormalities are recorded at each subsequent ophthalmological examination. New or worsened abnormalities should be recorded as AE.

#### **6.3.10 Physical Examination (PE)**

Complete PE includes evaluation of the head, eyes, ears, nose, and throat, and the cardiovascular, dermatological, musculoskeletal, respiratory, and gastrointestinal systems. Breast, rectal, and genitourinary exams are performed as clinically indicated.

Limited PE includes cardiovascular, respiratory, and gastrointestinal systems; further symptom-directed examination may also include any other pertinent system as required.

Abnormalities observed at baseline, as well as new or worsened clinically significant abnormalities at all other visits, will be recorded on the electronic CRF. New abnormal PE findings will be followed up at the next scheduled visit. New or worsened abnormalities should be recorded as AE on the AE electronic CRF if considered clinically significant in the Investigator's opinion.

## **6.3.11 Other Safety Assessments**

#### 6.3.11.1 Pregnancy Test

Serum pregnancy tests will be performed for all females of childbearing potential at scheduled visits (refer to the Schedules of Assessments in the protocol for scheduled visits).

Protocol No. AL002-2 Last Revision Date: 12 Aug 2025

#### 6.3.11.2 COVID-19

Impact of coronavirus disease 2019 (COVID-19) on consent, scheduled visits, essential on-site assessments and remote visits (via phone or video), COVID-19 related AEs and participant withdrawals will be collected throughout the study.

#### 6.4 Pharmacokinetic (PK) Endpoints

- Serum PK concentrations of AL002
- CSF PK concentrations of AL002 (when available)

## 6.5 Exploratory PD Biomarker Endpoints

- CFBs in levels of sTREM2 in CSF and/or plasma
- CFBs in levels of biomarkers related to microglia function in CSF and/or plasma including but not limited to CSF1R, IL1RN, osteopontin, YKL-40
- CFBs in levels of biomarkers related to AD pathology in CSF and/or plasma including but not limited to Aβ40, Aβ42, pTau, tTau
- CFBs in levels of neurodegeneration biomarkers in plasma and CSF including but not limited to NfL
- CFBs in brain volume, assessed by volumetric MRI
- CFBs in brain pathological tau burden as assessed by Tau PET (for participants who agree to participate in the optional assessment only)
- CFBs in brain amyloid burden as assessed by longitudinal Amyloid PET scanning (for participants who agree to participate in the optional assessment only)

#### 6.6 Immunogenicity Endpoints

- Incidence of ADAs
- Titer results of ADAs

Protocol No. AL002-2 Last Revision Date: 12 Aug 2025

#### 7. STATISTICAL ANALYSIS

## 7.1 General Data Handling Rules and Definitions

All analyses will combine data from all participants in Part 1 and Part 2, unless otherwise specified.

Unless otherwise specified, when specifying for summaries and analyses, "treatment group" refers to each individual AL002 15 mg/kg, 40 mg/kg, and 60 mg/kg treatment group, and the placebo group. "AL002 40 and 60 mg/kg combined group" refers to the group pooling AL002 40 mg/kg and 60 mg/kg treatment groups. "Total AL002 group" refers to the group pooling AL002 15 mg/kg, 40 mg/kg, and 60 mg/kg treatment groups. And "overall" refers to the group pooling AL002 15 mg/kg, 40 mg/kg, and 60 mg/kg treatment groups, and the placebo group.

All assessments will be provided in respective by-participant data listings, except data collected only for confirmation of study entry criteria and for study administrative purposes. If any randomized participant is found to not have valid documented informed consent, that participant's data will be excluded from the report, except as necessary to document the error. By-participant data listings will be presented for all participants in the ARS and sorted by randomized treatment, actual treatment, participant identification (ID) number, visit date, and time (if applicable), unless otherwise specified. Data collected on log forms, such as AEs, will be presented in chronological order within the participant. Age, sex at birth, race, and ethnicity will be included in the listings.

All analyses will be conducted using SAS® version 9.4 or later.

Except where specified, all continuous variables will be summarized with descriptive statistics (the number of non-missing values, mean, standard deviation (SD), median, 25% quartile (Q1), 75% quartile (Q3), minimum (min) and maximum (max)) and all categorical variables will be summarized with frequency counts and percentages, by treatment group.

Missing data will be maintained as missing, unless specified in Section 7.4.1.

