3.1.2. Study Objectives

The objectives of this Phase 2 study are the assessment of the efficacy and safety of IV AL002 treatment for up to 96 weeks. Multiple dose levels of AL002 will be studied against placebo at a dosing frequency of every 4 weeks. Participants with the *APOE* e4/e4 genotype who were enrolled under Versions 1–4 of this protocol will not receive any further study drug treatment, but should continue with the remaining planned visits in the Schedules of Assessments (Section 14.1).

Efficacy will be assessed with clinical outcome assessments (COAs) as well as fluid and imaging biomarker measures. Safety will be assessed through monitoring of AEs (including AESI and SAEs), changes in laboratory and vital sign values, incidence of findings from physical, neurological, ECG, MRI and ophthalmological exams, and reports of suicidal ideation or behavior. PK in both the serum and CSF will be assessed for investigation of exposure-response and exposure-safety relationships. Blood biomarker and MRI biomarker measures will be assessed for all participants.

In this study, several optional PD assessments will be performed for those participants who consent to the assessments. These include CSF collection for fluid biomarkers (except for Part 1, where CSF collection is mandatory for all visits), PET imaging with the tau radiotracer [18F]MK-6240, longitudinal Amyloid PET imaging, and/or speech assessment with the Winterlight Labs Speech Assessment (WLSA).

AL002 Alector, Inc.

3.1.3. Enrollment in Part 1 and Part 2

In Part 1, each dose level tested will consist of a minimum of 10 participants. Approximately 40 participants will be randomized at a 1:1:1:1 ratio to receive either AL002 15 mg/kg, 40 mg/kg, 60 mg/kg, or placebo, administered via IV infusion every 4 weeks. The remainder of the study will be enrolled as Part 2 which will include approximately 288 participants. The allocation ratio in Part 2 will also be 1:1:1:1. Participants randomized after July 2021 to receive 40 or 60 mg/kg will be titrated to their target randomized dose level over the first 2 or 3 doses, respectively, and then continue at their randomly assigned dose for the remainder of study participation. There will be no change to dose for participants randomized to receive 15 mg/kg or placebo.

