Participants in Part 1 with MRI evidence of ARIA at the Day 15 or Day 43 MRI will be discontinued from study drug administration. Participants in Part 1 with ARIA after Day 43 and participants in Part 2 with MRI evidence of ARIA at any visit will be managed according to the guidelines in Table 7.

AL002 Alector, Inc.

Table 7: Dosing Guidelines for ARIA

Finding	Asymptomatic/Symptomatic	Action	
Milda ARIA-E	Asymptomatic or Symptomatic	Suspend dosing until resolution of ARIA-E or	
Moderate ^b ARIA-E	Asymptomatic or Symptomatic	stabilization of ARIA-H. After resolution (ARIA-E) and/or stabilization (ARIA-H), if	
Severe ARIA-E	Asymptomatic or Symptomatic	participant dosing is restarted, they must receive the same dose they received immediately prior	
Mild or Moderate ARIA-H	Asymptomatic	to the ARIA-E/ARIA-H findings and continue on that dose for the remainder of the study. After resuming dosing, 5-10 days before their second post-resumption dose, participants must undergo an unscheduled MRI that must be assessed by the Central Reader for ARIA-E/H before the next dose is administered.	
		For mild or moderate symptomatic ARIA-E the use of oral or IV steroids can be considered.	
		For severe symptomatic ARIA-E it is recommended to hospitalize the participant for close observation and consider the use of IV steroids such as high-dose dexamethasone or a similar agent.	
Mild or Moderate ARIA-H	Symptomatic	Permanently discontinue treatment	
Severe ARIA-H	Asymptomatic or Symptomatic	Permanently discontinue treatment	
Serious ^c ARIA-E or Serious ARIA-H	Symptomatic	Permanently discontinue treatment	
Serious ^c ARIA-E or Serious ARIA-H	Asymptomatic	Suspend dosing until resolution of ARIA-E or stabilization of ARIA-H. After resolution (ARIA-E) and/or stabilization (ARIA-H), if participant dosing is restarted, they must receive the same dose they received immediately prior to the ARIA-E/ARIA-H findings and continue on that dose for the remainder of the study. After resuming dosing, 5-10 days before their second post-resumption dose, participants must undergo an unscheduled MRI that must be assessed by the Central Reader for ARIA-E/H before the next dose is administered.	
A second occurrence of ARIA-E after full resolution of a prior occurrence of ARIA-E	Asymptomatic or Symptomatic	Permanently discontinue treatment	

ARIA-E=amyloid-related imaging abnormality-edema; ARIA-H=amyloid-related imaging abnormality-hemosiderin deposits; MRI=magnetic resonance imaging.

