8.3.4. Safety Analyses

Safety analyses will be performed based on the Safety Set and participants will be assigned according to treatment actually received. If a participant is randomized to placebo and receives any amount of AL002, they will be included in the AL002 dose group based on the dose received.

All safety analyses at the completion of the study will be presented with data from Parts 1 and 2 combined. AEs will be coded using the MedDRA Version 23.0 or later. They will be summarized by system organ class and preferred term. Severity of the AEs, their relationships to treatment, SAEs, events leading to study drug withdrawal will be summarized similarly.

AL002 Alector, Inc.

The following endpoints will be summarized:

• Incidences of AEs, AESI, SAEs, AEs leading to study drug withdrawal, and death

- Changes from baseline in clinical laboratory tests over time, as appropriate
- Changes from baseline in 12-lead ECG results
- Incidences of MRI safety findings
- Incidences of physical, ophthalmological, and neurologic examination abnormalities
- Changes from baseline in vital signs over time and incidence of abnormal vital signs
- Incidences of suicidal ideation, suicidal behavior, and self-injurious behavior without suicidal intent, as determined using the C-SSRS
- Immunogenicity as assessed by incidence of ADAs during the study relative to the prevalence of ADAs at baseline, and impact upon safety, efficacy, and PK findings
- ECGs being read centrally will be analyzed and reported in a separate report

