#### 3.1.4 Treatment Administered

All participants in Part 1 and Part 2 will receive study treatment (placebo, 15 mg/kg AL002, 40 mg/kg AL002, or 60 mg/kg AL002). Study drug administration will begin on Day 1 visit and then will occur once every 4 weeks for the duration of the treatment period according to the Schedules of Assessments in the protocol.

In order to maintain the blind across all dose groups and allow step titration to the higher doses, the starting dose for each participant randomized to receive AL002 will be 15 mg/kg (or placebo) for the first study drug administration on Day 1 visit. For the second study drug administration, the dose will increase to 40 mg/kg for participants randomized to receive 40 mg/kg or 60 mg/kg, while doses in the other 2 groups will remain constant. For the third study drug administration, the dose will increase to 60 mg/kg for participants randomized to receive 60 mg/kg while doses in the other 3 groups will remain constant. The titration algorithm is provided in below Table 3-1.

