#### 5.2 As-Treated Set (ATS)

The ATS will consist of all participants who received any study treatment. All analyses using the ATS will group participants according to the actual treatment received.

If a participant is randomized to any dose level of AL002 and receives any amount of AL002, they will be analyzed at the highest dose level of AL002 received by the participant. Especially for participants who went on the dose titration algorithm (Table 3-1), their actual treatment received will be determined based on their Exposure – IV electronic CRF records and the participant visit dispensing history in the Interactive Response Technology (IRT) system.

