APOE genotype, time to the first occurrence, resolution, time to resolution, and reoccurrence will be summarized for participants with ARIA-E. APOE genotype and time to the first occurrence will be summarized for participants with post-baseline new ARIA-H.

The number and percentage of participants who had a post-baseline ARIA-E but did not have a new ARIA-H any time post-baseline will be summarized. The number and percentage of participants who had a new ARIA-H but did not have an ARIA-E any time post-baseline will be summarized. Similarly, the number and percentage of participants who had a new ARIA-H and an ARIA-E any time post-baseline will be summarized.

All the MRI summaries described above will also be provided separately for participants with the following APOE genotype(s) (1) e4/e4, (2) e4 carriers (including e2/e4, e3/e4 and e4/e4), (3) non-e4 carriers (excluding e2/e4, e3/e4 and e4/e4), and (4) e4 heterozygous carriers (including e2/e4 and e3/e4).

The Kaplan-Meier curve for the time to the first occurrence of ARIA-E will be plotted. For participants experienced at least one ARIA-E, the time to the first occurrence of ARIA-E is the time from the first dose date to the onset date of the first ARIA-E occurrence. For participants who did not experience ARIA-E, the censor date will be the earlier date of the last MRI scan date and the last dose date plus 90 days. Similarly, the Kaplan-Meier curve for the time to the first occurrence of new ARIA-H will be plotted.

All MRI findings will be listed.

Protocol No. AL002-2 Last Revision Date: 12 Aug 2025

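### No planned safety or ARIA summary separates titrated from untitrated 40 and 60 mg/kg participants, so none reports the ARIA rate of the titrated regimen

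*SAP*

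**What the plan says.** **Pooling.** SAP 7.1 states "All analyses will combine data from all participants in Part 1 and Part 2, unless otherwise specified". Protocol 8.3.4 says the same for safety: "All safety analyses at the completion of the study will be presented with data from Parts 1 and 2 combined".

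**Who is titrated.** Protocol 3.1.3: "Participants randomized after July 2021 to receive 40 or 60 mg/kg will be titrated to their target randomized dose level". For the other two groups, "There will be no change to dose for participants randomized to receive 15 mg/kg or placebo". Protocol 3.3.3 carries the same date limit. SAP 5.2 also recognises a subset: "Especially for participants who went on the dose titration algorithm (Table 3-1), their actual treatment received will be determined" from the exposure CRF and the IRT dispensing history.

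**Columns and subgroups.** SAP 7.5 tabulates safety by dose group, by 40 and 60 mg/kg combined and by total AL002, mainly in the Non-e4/e4 Set. SAP 7.5.7 gives ARIA-E and new ARIA-H by visit, overall and by radiographic severity, with time to first occurrence and Kaplan-Meier curves. It repeats the MRI summaries for four APOE genotype groupings. SAP 7.5.2 tabulates adverse events leading to discontinuation. SAP 7.9 adds swim lane plots for the e4/e4 Set only.

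**Text without a date limit.** SAP 3.1.4 says "the starting dose for each participant randomized to receive AL002 will be 15 mg/kg (or placebo) for the first study drug administration". Protocol 3.1.4 and 5.2 describe a 15 mg/kg start in similar terms.

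**The concern.** Protocol 1.3 presents titration as risk mitigation, in the section that reports ARIA as observed in this study. Protocol 1.4 expects the trial to inform dose selection for Phase 3. One of the main safety questions is therefore how often ARIA occurs at 40 and 60 mg/kg when the dose is stepped up. A column that mixes participants who started at the full dose with participants who started at 15 mg/kg describes neither regimen.

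The SAP also takes precedence over the protocol where they differ (SAP 1). A reader who relies on SAP 3.1.4 would take the pooled columns to be fully titrated.

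**Working it through.** **1. Is any summary defined by titration?** I went through the outputs in SAP 7.5, 7.5.2, 7.5.7 and 7.9. The factors used are dose group, visit, severity and genotype. None is titration status, randomization date or first dose received. The list of changes in SAP 9 does not mention it. MRI findings and exposure are listed by participant, so a rate could be counted by hand, but none is planned.

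**2. Denominator.** Protocol 8.1 starts from 70 per group and adds 15 + 6 + 27 = 48 participants over four groups: 70 + 48/4 = 82 per group, and 4 x 82 = 328 = 40 (Part 1) + 288 (Part 2). The planned size reproduces. The main safety tables exclude e4/e4 participants, so actual columns will be somewhat smaller.

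**3. What pooling does.** Let w be the untitrated share of a column, p_u the untitrated ARIA rate and p_t the titrated rate.

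- Pooled rate = w x p_u + (1 - w) x p_t
- Pooled rate - p_t = w x (p_u - p_t)

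The documents give none of w, p_u and p_t. All values below are assumed. With 5, 10 or 20 untitrated of 82, w is 6.1%, 12.2% or 24.4%.

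| Assumed p_u vs p_t | 5 of 82 | 10 of 82 | 20 of 82 | Gap from p_t (points) |
|---|---|---|---|---|
| 40% vs 20% | 21.2% | 22.4% | 24.9% | +1.2, +2.4, +4.9 |
| 40% vs 10% | 11.8% | 13.7% | 17.3% | +1.8, +3.7, +7.3 |
| 20% vs 20% | 20.0% | 20.0% | 20.0% | 0 |
| 10% vs 20% | 19.4% | 18.8% | 17.6% | -0.6, -1.2, -2.4 |

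**4. The highest-dose rule.** SAP 5.2, which SAP 5.3.3 applies to the Non-e4/e4 Set, places a participant at the highest AL002 dose received. Under the titration table (SAP Table 3-1), someone randomized to 60 mg/kg who stops after dose 1 has received 15 mg/kg and is counted there. An untitrated participant who stops after a first dose of 60 mg/kg is counted under 60 mg/kg. Early events therefore go to different columns depending on regimen. A titration split made inside the as-treated columns would lose the earliest events of titrated participants.

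**5. Part is a different boundary.** Early MRIs fall on Days 15 and 43 in Part 1 (Protocol 3.1.10), and 5-10 days before Doses 2, 3 and 4 in Part 2 (Protocol 6.5.12). On stopping, Protocol 7.11.1.2 says "Participants in Part 1 with MRI evidence of ARIA at the Day 15 or Day 43 MRI will be discontinued from study drug administration", while Part 2 follows Table 7, which for several findings suspends dosing with possible restart. These differences follow Part, whereas titration follows randomization date. The documents do not say that the two boundaries coincide.

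**The case against.** Pooling the Parts was prespecified in the protocol. The tables are descriptive, so no test or primary conclusion changes. Listings are available, Protocol 8 allows additional analyses, and SAP 7.6 mentions possible exploration of exposure against safety. No untitrated count is given, and the existence of such participants is inferred from the date limit and from SAP 5.2. The main tables exclude e4/e4 participants, which may shrink the untitrated group further, so a separate column could hold only a handful per arm.

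Most of this limits the size of the point, and that part stands. It does not remove the gap. A listing gives no rate, a permission to add analyses is not a plan to do so, and leaving out e4/e4 participants does not take untitrated participants of other genotypes out of the 40 and 60 mg/kg columns.

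A reader might go further and infer that the pooled rate overstates ARIA under titration. The documents do not support that, since the sign depends on rates they do not report. Nor do they support treating a Part 1 versus Part 2 split as a titration split, or deciding that SAP 3.1.4 is the passage in error.

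**Conclusion.** The point holds in this form: titrated and untitrated 40 and 60 mg/kg participants share every planned safety and ARIA summary, and no planned table or figure gives the ARIA rate of the titrated regimen. Neither the size nor the direction of any distortion can be determined. The range of -2.4 to +7.3 points per arm rests wholly on assumed counts and rates. The conclusion assumes that some participants at these doses were randomized before the date limit, as Protocol 3.1.3 and 3.3.3 and SAP 5.2 imply. It does not touch the primary efficacy analysis. It is a cheap improvement to the reporting of an identified risk.

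**What to change.** - In SAP 7.5.7, derive titration status from randomization date and the actual first dose in the exposure and IRT records. SAP 5.2 already uses these records to assign treatment.
- For the 40, 60 and combined groups, defined by **randomized** dose so that early stoppers are not moved to a lower column, repeat ARIA-E and ARIA-H incidence and time to first occurrence by titration status. Do the same in SAP 7.5.2 for adverse events leading to discontinuation.
- Show placebo participants randomized in the same calendar period as the comparator. They are not titrated, so this needs randomization date and not the dose record.
- Add a note that the early MRI schedule and the Day 15/43 discontinuation rule differ by Part, and that the titration split does not necessarily separate them.
- Reconcile Protocol 3.1.4 and 5.2 and SAP 3.1.4, which give a 15 mg/kg start with no date limit, with Protocol 3.1.3 and 3.3.3 and SAP 5.2.

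Cost: a derived flag, a placebo period variable and a few repeated tables and figures. The untitrated columns may be small and imprecise.
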